The University of Texas Medical Branch at Galveston

Research Protocol # 15-0272

Title: Induction of labor in women with unfavorable cervix: randomized control study comparing Dilapan to Foley bulb.

NCT02899689

October 24th 2016

1. Introduction and Purpose: Historically, mechanical methods were the first methods developed to ripen the cervix or to induce labor (Thiery 1989). Dilapan®, a hygroscopic cervical dilator made of a patented hydrogel (AQUACRYL), works by stimulating the release of endogenous prostaglandins, which degrade collagen fibers and soften the cervix. Additionally, it dilates the cervix gradually and the effect is gentle as well as predictable. Recently, Dilapan, another form of mechanical dilator, has been approved by the FDA. There are no data comparing this newly approved Dilapan® to the most commonly used mechanical dilator method which is the foley bulb. Therefore, we propose a randomized controlled trial to determine the effectiveness of Dilapan® compared with foley bulb for cervical ripening and induction of labor in pregnant women greater than 37 weeks.

2. Background: Labor induction is a common obstetric procedure, which is generally carried out when the risks of continuing pregnancy outweigh the benefits. To maximize the success of induction of labor in women with an unfavorable cervix, various ripening methods are available. These include drugs such as prostaglandins and mechanical agents such as the foley bulb cervical dilator, which has been used in labor delivery units for decades. Mechanical methods of labor induction are safe, effective and cost effective. Recently, Dilapan® was approved by the FDA as another form of mechanical dilators. Data are lacking regarding the comparative effectiveness of Dilapan® compared with the standard foley bulb in labor induction.

3. Concise Summary of Project: Primary outcome will be to compare the efficacy of achieving a vaginal delivery using the synthetic osmotic cervical dilator Dilapan-S® versus Foley catheter for cervical ripening prior to induction of labor. Secondary outcomes will be to evaluate the efficacy of Dilapan-S® versus Foley catheter on other clinical outcomes such as vaginal delivery rate within 24 and 36 hours post insertion, time to reach active stage of labor defined as ≥ 6 cm, change in Bishop score, rate of spontaneous and operative vaginal delivery, rate of caesarean sections and patient satisfaction. Randomization will be performed using a computer generated random list of numbers assigning subjects to the 2 groups of the study. This list of random number assignments will be kept secure in an opaque envelope until the end of the study.

4. Study Procedures:

After institutional review approval, pregnant women that are scheduled for induction of labor will be approached by principal investigator or any of the co-investigators for participation in the study in a private subject room in labor and delivery unit. Prospective subjects presenting for induction of labor in labor and delivery, and willing to participate in the study will be evaluated for their eligibility including, including their bishop score. The latter will be obtained from the subject chart after the initial pelvic exam which is standard of care for these subjects in our unit. After obtaining informed consent, subjects will be randomized.

Group assigned to receive synthetic osmotic cervical dilator:

Before the device placement, patients undergo continuous CTG monitoring for 20 minutes while fetal condition and uterine activity are monitored. The cervix is visualized with a sterile vaginal speculum and cleaned with iodine. As many as possible pieces of synthetic osmotic cervical dilator (Dilapan-S®, Medicem Technology, Kamenne Zehrovice, Czech Republic) are inserted into the cervical canal under direct visualization. Synthetic osmotic dilators are entered to the cervical canal with special attention to cross through the internal os. The number pieces inserted will vary, since different patients will have different pelvic or cervical exam/dilatation. Synthetic osmotic dilators will be inserted as per manufacturer's instructions for use /Appendix 2/. The patient will be instructed to report any excessive bleeding, pain or other concerns. Under no circumstances should patient try to remove Dilapan-S® herself.

The synthetic osmotic dilators will be left in place for at least 12 hours, and no longer than 24 hours. Patient will be allowed to ambulate, shower and perform regular activity as long as a reactive and reassuring NST is documented after placement of device. Reasons for examining or removing dilators earlier include: 1) Spontaneous onset of labor (defined as regular, firm, uterine contractions with an effaced cervix >80% and a cervical dilatation > 3 cm); 2) Category III fetal heart rate tracing; 3) Spontaneous rupture of membranes or need for amniotomy; 4) Spontaneous expulsion of dilators. If cervix remains unfavorable after extraction of the dilators (< 3cm and at most 60% effaced) to provide induction of labor, the second round of Dilapan-S® will be used in this case for maximum of 12 hrs. If cervix remains unfavorable after extraction of second round of cervical dilator, only pharmacological cervical ripening may be provided. Neither Dilapan-S® or Foley will be used in this case. The agent and its total dose will be recorded into the data sheet.

Group assigned to receive Foley catheter:

Before the device placement, patients undergo continuous CTG monitoring for 20 minutes while fetal condition and uterine activity are monitored. The cervix is visualized with a sterile vaginal speculum and cleaned with iodine. A Foley catheter is introduced into the cervix and the balloon is filled with 60 ml of sterile 0.9% NaCl. The Foley catheter will be left in place for at least 12 hours, and no longer than 24 hours. Patient will be allowed to ambulate, shower and perform regular activity as long as a reactive and reassuring NST is documented after placement of device. Reasons for examining or removing Foley catheter earlier included: 1) Spontaneous onset of labor (defined as regular, firm, uterine contractions with an effaced cervix >80% and a cervical dilatation > 3 cm); 2) Category III fetal heart rate tracing; 3) Spontaneous rupture of membranes or amniotomy; 4) Spontaneous expulsion of Foley catheter. If cervix remains unfavorable after extraction of the dilators (< 3cm and at most 60% effaced) to provide induction of labor, a second round of Foley catheter will be used in this case for a maximum of 12 hrs. If cervix remains unfavorable after extraction of second round of cervical dilator, only pharmacological cervical ripening may be provided. Neither Dilapan-S® or Foley will be used in this case. The agent and its total dose will be recorded into the data sheet.

Induction of labor:

After expulsion or removal of synthetic osmotic dilators or Foley catheter, induction of labor using either oxytocin infusion or prostaglandins may be performed. Total dose of oxytocin and prostaglandins used will be documented. The oxytocin protocol used in our labor and delivery consists of: oxytocin infused intravenously through a controlled infusion pump at a proximal port on the peripheral IV line. Oxytocin is started at 2 milliunits/min and increased at a rate of 2 milliunits/min or less every 10 minutes until adequate contraction pattern is achieved. Initial maximum dose is 20 milliunits/min. Dose can be increased to 30 milliunits/min after faculty staff approval. Prostaglandins in practice in our facility include: Prepidil: dinoprostone 0.5 mg/3 g (2.5 mL gel), Misoprostol (buccal, sublingual or vaginal) 25 mcg tablets or Cervidil: dinoprostone 10 mg vaginal insert.

The study will be explained as in the consent form and if agreed, subjects will elect either to or not to participate in the study after all risks and benefits are explained. Data to be collected will consist of age gravida/para, gestational age, BMI, time of date of intervention, time date of delivery, mode of delivery, bishop score at admission, bishop score after 12 hrs. of intervention, time and date of rupture of membranes, vaginal delivery within 24 hrs., hospital length of stay, other intrapartum and obstetrical interventions, complications in labor and delivery including but not limited to infections, hemorrhage, fetal decelerations and subject satisfaction. Data will be abstracted from subjects medical records as well as from direct interview with the subject. We will also collect basic neonatal data including birth weight, Apgar scores, rate of admission to neonatal intensive care unit, infections, and other neonatal complications. If elected to participate consents will be obtained and stored in subject chart. A copy of the consent will be given to the subject. Subjects will be consented in either English or Spanish by research personnel familiar with the language. Randomization will be done at time of consents. The study's time frame inclusive will be from 2016 till 2018. Data will be analyzed as per intent to treat.

Sample Size Calculation

The sample size will be calculated for the non-inferiority test.

The significance level of the test is targeted at 0.025, one-sided.

The rate of overall vaginal delivery is 71% and 76% for Foley catheter and Dilapan-S® , respectively. Higher rates are better.

The non-inferiority margin is $\delta=10\%$. It is defined as the largest treatment difference of no clinical importance.

The treatment allocation ratio will be 1:1.

The power of the non-inferiority test to be achieved is 90%.

Based on the above assumptions, the sample size would be 182 evaluable subjects in either treatment group, i.e. 364 evaluable subjects in total. Assuming that 13% of patients will not qualify for the primary analysis set (due to protocol deviation or considered as drop-out of loss to follow up), 420 patients are to be enrolled into this study.

5. Sub-Study Procedures: Not applicable.

6. Criteria for Inclusion of Subjects:

- Pregnant woman scheduled for induction of labor
- Age between 18 and 45 years
- Understanding and capable to sign informed consent
- Singleton pregnancy
- Gestational age ≥ 37 ^{0/7}weeks
- Live fetus in cephalic presentation
- Intact membranes
- Pelvic exam (sterile vaginal exam) of less than or equal to 3cm and at most 60% effaced.

7. Criteria for Exclusion of Subjects:

- Iodine allergy
- Active labor or oxytocin has been administered
- Chorioamnionitis
- Prior uterine or cervical surgery
- Non reassuring fetal status requiring immediate delivery
- Non-cephalic fetal presentation
- Active vaginal bleeding from cervical os
- Placenta previa
- EFW > 5000 gm (non diabetic) or > 4500gm (diabetic)
- ⚡ Other contraindication to vaginal delivery

8. Sources of Research Material: Medical chart/records.

9. Recruitment Methods and Consenting Process: After institutional review approval, pregnant women scheduled for induction of labor will be approached by perinatal research division staff (PRDS) for participation in the study. Prospective subjects presenting for induction of labor in labor and delivery unit, and willing to participate in the study will be evaluated for their eligibility including their pelvic

exam. The latter will be obtained from the subject chart after the initial pelvic exam which is standard of care for these subjects in our unit. The study will be explained as in the consent form and if agreed, subjects will elect either to or not to participate in the study after all risks and benefits are explained. If willing to participate, written consent will be obtained and a copy placed in patient chart. A copy of the consent will be given to the subject. Subjects will be consented in either English or Spanish by research personnel familiar with the language. Randomization will be done after obtaining consent. Participants are randomly allocated to cervical ripening with either a synthetic Dilapan-S® or Foley catheter. The randomization sequence is created using a computer generated randomization scheme with 1:1 allocation for each arm of the study. The random allocation sequence is concealed from those responsible for recruiting participants into the study by keeping it in a file cabinet with access restricted to research staff. PRDS will disclose the nature of the assignment only after patient's consent.

10. Potential Risks:

- a. Accidental release of confidential subject information
- b. Vaginal bleeding during/after study device's insertion
- c. Subjective pain felt during insertion
- d. Vaso-vagal reaction from manipulation of the cervix
- e. Contamination of the device during insertion
- f. Allergic reaction from hypersensitivity to the components
- g. Rupture of membranes or uterine contractions as the feature of the onset of labor
- h. Cervix laceration if study device inserted using an incorrect technique
- i. Retraction of the device to the uterine cavity if inserted using an incorrect technique
- j. Entrapment of the device if removed using an incorrect technique
- k. Fragments of the device in the genital tract if removed using an incorrect technique

11. Subject Safety and Data Monitoring: We believe that this intervention confers minimal risk to the subject that participates in this study. One group will be randomized to our standard cervical mechanical dilator at our institution. Adverse events may include rupture of membranes, pain/discomfort, vaginal bleeding. Data will be monitored through chart review and the subject ID will be protected by de-identification. Data will be stored on a UTMB password-protected computer in a locked room.

12. Procedures to Maintain Confidentiality: Each subject will be assigned a study number with personally identifiable information deleted or removed. If needed, charts will be reviewed in the medical records area. Subjects' information will be de-identified and tagged with a number. Data will be collected and stored on a UTMB password-protected computer in a locked room.

13. Potential Benefits:

This study has the potential benefit to show that pre-induction cervical ripening with Dilapan-S® may increase the rate of overall vaginal deliveries as well as the rates of vaginal deliveries reached within 24 and 36 hours. Another benefit is that it may confirm the safety of Dilapan-S® use as compared to foley catheter cervical ripening. In addition, we believe that subject's satisfaction may be improved, since Dilapan-S® can be placed as an outpatient, and may shorten hospital length of stay. Ultimately, this will reduce the health care costs associated with failed induction (cesarean delivery) and improve maternal neonatal early bonding. We hope that the results of this study will show that Dilapan-S® is a reasonable alternative to Foley catheter cervical ripening in the United States.

14. Biostatistics:

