Rate of vaginal deliveries within 24 hours, rate of vaginal deliveries within 36 hours, rate of spontaneous vaginal deliveries, rate of operative vaginal deliveries and rate of caesarean sections will be analysed using similar statistical methods as described above for the primary endpoint, except for the definition of the non-inferiority margin and for the non-inferiority test. The 95% 2-sided CIs will be calculated for the treatment differences.

Time to reach active stage of labour defined as ≥ 6 cm (mins) will be analysed using survival analysis methods. Detailed methodology including set-up of censored values will be described in the final SAP. Change in Bishop score from baseline will be summarised by treatment group.

All rates above, time to reach active stage of labour and Bishop score are related to the secondary objectives and simultaneously, they are supportive measurements related to the primary objective. Patient satisfaction associated with the device used for cervical ripening (Patient Satisfaction Survey, question No. 12) will be evaluated as a secondary objective. Counts and proportions in all categories will be presented by treatment group. The location shift in response categories between the two treatment groups will be calculated and tested at the $\alpha = 0.05$ level of significance, two-sided.

Exploratory Variables Analysis

Exploratory variables will be summarised by treatment group.

Safety Variables Analysis

Safety variables will be summarised by treatment group.

Procedure for Accounting for Missing Data

Study subjects with missing primary variable will be evaluable neither for the ITT nor for the PPS population.

Missing primary variable data is expected to be very rare. If not, a different procedure may be refined in the SAP (e.g. a conservative imputation technique or sensitivity analyses) with the knowledge of the clinical data.

Procedure for Protocol Deviations

All protocol deviations will be listed by treatment group. Study subjects with a major protocol deviation will be excluded from the PPS analysis which makes demonstration of lack of sensitivity to protocol deviations possible (robustness).

Procedures for Deviations from the Original Statistical Plan

The SAP will contain more detailed description of the statistical analysis. If a need to change procedures of the analysis arises, an appropriate SAP update will be made. Major changes will require a protocol amendment.

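### The instruction to report bleeding and pain is written for the Dilapan-S arm only, which leaves spontaneous reports of these two events open to unequal ascertainment

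*Combined protocol and SAP*

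**What the plan says.** Section 4 describes the two arms separately. For Dilapan-S, after the insertion steps, it states: "The patient will be instructed to report any excessive bleeding, pain or other concerns". A handling warning follows: "Under no circumstances should patient try to remove Dilapan-S® herself". The Foley description moves from filling the balloon straight to the dwell time, "The Foley catheter will be left in place for at least 12 hours, and no longer than 24 hours", with no counterpart to the reporting sentence. Both arms have the same freedom of movement once the device is in: "Patient will be allowed to ambulate, shower and perform regular activity as long as a reactive and reassuring NST is documented".

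Other provisions make no distinction by arm:
- The data-collection paragraph of section 4 lists, for every woman, "complications in labor and delivery including but not limited to infections, hemorrhage, fetal decelerations and subject satisfaction". The sources are the medical record and direct interview.
- Section 11 states: "Adverse events may include rupture of membranes, pain/discomfort, vaginal bleeding". Monitoring is by chart review.
- Section 13 hopes that "it may confirm the safety of Dilapan-S® use as compared to foley catheter cervical ripening".
- Section 14, Safety Variables Analysis, plans only this: "Safety variables will be summarised by treatment group".
- The last paragraphs of section 14 acknowledge that the study is open-label.

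**The concern.** Bleeding and pain are not particular to one device. Section 10 lists bleeding around device insertion and pain at insertion as study risks, and section 11 names both events without reference to arm. The sentence asking women to report them appears in one arm description only.

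Mild or moderate pain, and bleeding short of hemorrhage, reach a chart mainly when the woman mentions them or someone asks. If staff follow the text literally, one arm is prompted and the other is not, and in an open-label trial nothing offsets that. The by-arm safety table could then show more bleeding and pain with Dilapan-S when the true rates are equal, or could hide a true excess with Foley. What is at stake is how those two rows are read when the report addresses the hope expressed in section 13. An event that was never reported cannot be recovered from the chart afterwards.

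**Working it through.** **The plan's own figure.** The only design calculation is the sample size for vaginal delivery. With rates of 71% and 76%, margin 10 points, one-sided 0.025 and 90% power:

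n = (1.960 + 1.282)² × (0.71×0.29 + 0.76×0.24) / (0.05 + 0.10)² = 10.51 × 0.3883 / 0.0225 ≈ 181.3, so 182 per arm, as stated.

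The reporting instruction enters nowhere in this, and the endpoint does not depend on what a woman reports. No planned figure changes.

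**The two arm descriptions in section 4, side by side.**

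| Element | Dilapan-S | Foley |
|---|---|---|
| Monitoring before placement, speculum, iodine | yes | same |
| Dwell time 12 to 24 hours | yes | same |
| Ambulation, shower, regular activity | yes | same |
| Early-removal reasons | four listed | essentially the same four |
| Second round, up to 12 hours | yes | same |
| Told not to remove the device herself | yes (device-specific) | not stated |
| Told to report bleeding, pain, other concerns | yes (not device-specific) | not stated |

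**Does the common data collection close the gap?** Only in part. Section 4 gives both arms the same items and sources, but its list names hemorrhage, not lesser bleeding, and does not name pain. It gives the interview no adverse-event content and no timing. The Patient Satisfaction Survey in section 14 is described only through question 12, on satisfaction. Rupture of membranes, the third event in section 11, is better protected: its date and time are a data item for every woman, and it is an early-removal reason in both arms.

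**Possible size (assumptions only).** Let p be the true rate in both arms, and cD and cF the proportions captured with Dilapan-S and Foley. The false difference is p × (cD − cF). The documents supply none of these values.

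| p | cD | cF | False difference (points) |
|---|---|---|---|
| any | equal to cF | equal to cD | 0 |
| 5% | 100% | 80% | 1.0 |
| 10% | 100% | 80% | 2.0 |
| 20% | 100% | 80% | 4.0 |
| 20% | 80% | 60% | 16 − 12 = 4.0 |
| 20% | 90% | 50% | 18 − 10 = 8.0 |

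For scale, take 420/2 = 210 women per arm. For 16% against 12% the standard error is √[(0.16×0.84 + 0.12×0.88)/210] = 0.0338, so 4 points is about 1.2 standard errors. For 18% against 10% it is √[(0.18×0.82 + 0.10×0.90)/210] = 0.0336, so 8 points is about 2.4. A nominal two-sided 5% test would flag these about 22% and 66% of the time. The plan contains no such test, and the last row assumes that half of Foley events are missed.

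**The case against.** The strongest reply is that the Foley text is silent, not contrary. Foley is the institution's standard device, so routine counselling may have been left unwritten while steps for the newer device were spelled out. The sentence stands among device-handling steps and reads as patient care, not as the method of collecting adverse events. Consent precedes randomization and covers risks, and neither the consent form nor the manufacturer's instructions in Appendix 2 could be examined, so a common instruction may exist there. Items and sources are the same for both arms. Bleeding heavy enough to be called excessive is likely to be charted without prompting. Safety is not among the outcomes in section 3, and its analysis is descriptive.

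Most of this stands, and it limits the point. A reader might infer that Foley women are not told to report problems, that adverse events are collected by different methods in the two arms, or that the safety comparison is biased. The documents support none of these: the first rests on silence, the second conflicts with the common data-collection paragraph, and the third needs capture rates that appear nowhere.

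What the reply does not remove is the asymmetry itself. The one explicit prompt for pain and bleeding in the available text applies to one arm. Common sources do not equalize capture if women are prompted unequally, and a descriptive table by arm is still read as a comparison.

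**Conclusion.** The point holds in a limited form and is of low severity. If section 4 is followed as written, spontaneous reports of pain and bleeding are open to differential ascertainment. The likely direction is against Dilapan-S, assuming that prompting increases reporting. The size cannot be computed from the documents. On assumed true rates of 5% to 20%, full capture with Dilapan-S and 80% to 100% capture with Foley, it is 0 to 4 points, and it is zero if Foley women are in practice told the same. Larger figures need stronger assumptions about missed Foley events.

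Vaginal delivery, the sample size and objectively recorded outcomes such as Apgar scores and neonatal intensive care admission are not affected. The text supports saying that these two safety rows are open to bias, not that bias has been shown.

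**What to change.** 1. Reconcile the two arm descriptions in section 4 so that the reporting instruction is common to both.
2. In the data-collection paragraph of section 4, specify one scripted set of questions on bleeding and pain, worded identically and asked in both arms at device removal or expulsion, within the interview already planned.
3. In section 14, Safety Variables Analysis, state that the by-arm summaries of bleeding and pain are based on those answers.

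The cost is a sentence in the protocol and a few lines on the data sheet, with no extra visit. Recorded event counts in the Foley arm will probably rise, and the report should be ready to explain that.

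### The way the protocol says the randomisation list is kept and released does not assure allocation concealment

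*Combined protocol and SAP*

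**What the plan says.** Section 9 (Recruitment Methods and Consenting Process) claims concealment and names the method: the sequence is "concealed from those responsible for recruiting participants into the study by keeping it in a file cabinet with access restricted to research staff". It does not define research staff. The same section says that "pregnant women scheduled for induction of labor will be approached by perinatal research division staff (PRDS) for participation in the study" and that "PRDS will disclose the nature of the assignment only after patient's consent".

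Section 3 (Concise Summary of Project) describes the storage differently: "This list of random number assignments will be kept secure in an opaque envelope until the end of the study". Section 4 (Study Procedures) names different recruiters. There, women "will be approached by principal investigator or any of the co-investigators for participation in the study".

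On timing, Section 9 has "Randomization will be done after obtaining consent" and Section 4 has "Randomization will be done at time of consents". In both sections the examination used for eligibility is read from existing records; in Section 9 it is "obtained from the subject chart after the initial pelvic exam which is standard of care".

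Section 14 (Biostatistics) acknowledges that the study is open-label. It bases the primary conclusion on a 95% confidence interval for the difference in vaginal delivery rates in the per-protocol population, with the intention-to-treat population in support.

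**The concern.** Concealment works only if the person who decides whom to approach, and when, cannot know the next assignment. The protocol relies on restricted storage for this, but it describes the people with access by a term that, on an ordinary reading, covers the people who recruit. The second account, a sealed list, does not explain how anyone was to be assigned while it stayed sealed.

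What is at stake is comparability of the arms before any device is placed. A recruiter who has seen the next assignment can steer enrolment, even without meaning to, using facts already in the chart. The protocol's own Background treats an unfavourable cervix as bearing on the success of induction, so the recorded pelvic examination is a plausible basis for such steering. Any resulting shift would pass directly into the difference in rates, and so into both the non-inferiority and the superiority conclusion. Its direction cannot be known in advance.

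**Working it through.** No figure in the plan depends on how the list is held. The sample size (182 per group, 364 evaluable, 420 enrolled) is neither challenged nor changed. The check is a comparison of the sections.

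1. **Whom does the cabinet exclude?** Section 9 restricts access to research staff. PRDS are, by their title, staff of a research division, and Section 9 has them recruit and disclose. No sentence gives cabinet access to some research staff and withholds it from those who recruit. The claim that recruiters are kept from the sequence is therefore asserted, but the stated barrier does not deliver it.

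2. **Can the envelope supply assignments?** Section 3 describes one list and one envelope. There are two cases:
   - The list is opened at enrolment. Whoever reads off one assignment can then see those that follow, and the envelope was not closed until the end of the study.
   - The list stays sealed as a back-up. Assignments then come from something else, and no section says what.

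3. **Do the two accounts work together?** The envelope could sit in the cabinet. That settles where the list is kept, but not how the next assignment is taken from it without exposing the rest.

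4. **Who recruits?** Section 4 says the investigators; Section 9 says PRDS. Both may do so, but then both need to be kept from the list, and neither section says that they are.

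5. **What does the timing rule cover?** Sections 4 and 9 place randomisation at or after consent, and Section 9 places disclosure after consent. The woman therefore decides without knowing her arm. The rule does not govern what a recruiter may already know when choosing whom to approach.

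6. **Is a release step described elsewhere?** Sections 3, 4, 9 and 14 are the ones that touch on randomisation. None describes numbered sealed envelopes, a central or electronic service, a list-holder outside recruitment, or a log of releases.

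7. **Would the analysis repair it?** The per-protocol set is a subset of the intention-to-treat set, which is itself drawn from those randomised. Both start after entry, so neither undoes selection at entry. Section 14 describes a difference in proportions and mentions no covariate adjustment. Masking the statisticians protects the analysis, not the enrolment.

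**The case against.** The best defence is that Section 9 states the requirement outright. If research staff is read to include recruiters, its sentence contradicts itself, so the charitable reading is that access was meant for staff who do not recruit. That is a possible intention, and the text does not say that recruiters have access. But the same section gives recruitment and disclosure to PRDS without separating them from that group, so the ambiguity stands.

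Other safeguards deserve credit. There is an envelope as well as a cabinet, and Section 9 says who discloses and when. Section 14 promises baseline summaries by arm, a count of women screened but not randomised with reasons, and a listing of wrong assignments. These help, but a woman who was never approached need not appear in the screening count, and none of these reports prevents steering by someone who has seen the list.

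Three stronger inferences are tempting and are not supported:

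- A reader might infer that recruiters did see the list, or that enrolment was steered. The documents show exposure, not occurrence.
- A reader might infer that later assignments could be guessed from earlier ones because the trial is open-label. The documents mention no blocks or strata, so nothing in them supports this. The concern depends on someone having seen the list.
- A reader might infer that Sections 3 and 9 flatly contradict each other, or that there is no release procedure at all. They can be partly reconciled, and a discloser and a time are given. What is missing is release of one assignment without exposing the next.

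**Conclusion.** The point holds as a defect in the stated method and should be fixed. It is more than thin reporting: the protocol names a concealment method which, followed as written, does not keep later assignments from the people who recruit.

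No numerical size can be given. The documents contain nothing from which to estimate how far enrolment might be steered, in which direction, or with what effect on the vaginal delivery rate. Any figure would rest wholly on assumed inputs, so none is offered.

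The conclusion rests on two assumptions: that research staff carries its ordinary meaning and so may include PRDS, and that no separate randomisation procedure exists outside this document. If such a procedure exists and keeps recruiters from the list, the remaining task is to cite it and align the sections.

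**What to change.** Reconcile Sections 3, 4 and 9 so that they describe one mechanism:

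- Replace the accessible list with sequentially numbered, sealed opaque envelopes, or with an electronic randomisation module if one already exists. The envelopes may be kept in the locked cabinet.
- Open them in order, one per woman, and log each opening only after eligibility and consent are recorded.
- Have the master list held by an existing role that does not recruit. Say who research staff are and what the Section 3 envelope is for.
- Name the recruiting role or roles consistently.
- If enrolment has begun, document how assignments were actually held and released, and discuss this in the report. Section 14 already requires the report to discuss the risk that open-label conduct influenced the results.

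The cost is a short amendment and the work of preparing and logging the envelopes, at most 420 for the planned enrolment. No endpoint, sample size or clinical procedure changes. The documents do not say whether a module is available, but envelopes need none. The amendment cannot protect women already randomised; for them only documentation and discussion are possible.
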